#### 12.2.1.2. Serious Adverse Event

An SAE is any AE occurring at any dose and regardless of causality that:

- Results in death
- Is life-threatening
- Requires inpatient hospitalization or prolongation of existing hospitalization
- Results in persistent or significant incapacity or substantial disruption of the ability to conduct normal life functions
- Is a congenital anomaly or birth defect in an offspring of a patient taking study drug
- Is an important medical event

The term "life-threatening" refers to an event in which the patient was at immediate risk of death at the time of the event. It does not refer to an event that hypothetically might have caused death if it were more severe.

Important medical events are those that may not meet any of the criteria defined above; however, they may be considered serious when, based upon appropriate medical judgment, they may jeopardize the patient and may require medical or surgical intervention to prevent one of the other outcomes listed in the SAE definition.

Pregnancy is not considered an AE; however, information will be collected for any pregnancies that occur during the study (from the time of first dose of study drug until the final visit). Certain pregnancy outcomes will require submission as an SAE (Section 9.7.3).

The investigator is responsible for reporting to the Sponsor or its designee all AEs and SAEs that are observed or reported by the patient during the study (from the time of first dose of study drug until the final visit), regardless of their relationship to study drug or their clinical significance. All SAEs reported or observed during the study must be followed to resolution or until the investigator deems the event to be chronic or the patient to be stable. The Sponsor or its designee may contact the investigator to obtain additional information on any SAE that has not resolved at the time the patient completes the study.

# 12.3. Eliciting Adverse Event Information

At every study visit, patients must be asked a standard, non-directed question, such as, "How do you feel?" or "How have you been feeling since your last visit?", to elicit any medically related changes in their well-being. They will also be asked if they have been hospitalized, had any accidents, used any new medications, or changed concomitant medication regimens (including prescription drugs, over-the-counter medications, vitamins, herbal products, and minerals). Responses should be recorded in the source documents.

In addition to patient observations, AEs must be documented for any clinically significant diagnosis resulting from abnormal laboratory test values, physical examination findings, ECG abnormalities, or other documents that are relevant to patient safety.

# 12.4. Assessment of Causality

The investigator must use the following classifications and criteria to characterize the relationship or association of the study drug in causing or contributing to the AE:

- Unrelated: This relationship suggests that there is no association between the study drug and the reported event.
- Unlikely: This relationship suggests that the temporal sequence of the event with study drug administration makes a causal relationship improbable and/or other factors also provide plausible explanations.
- Possible: This relationship suggests that treatment with the study drug caused or contributed to the AE. That is, the event follows a reasonable temporal sequence from the time of study drug administration and/or follows a known response pattern to the study drug but could have been produced by other factors.
- Probable: This relationship suggests that a reasonable temporal sequence of the event with study drug administration exists and, based upon the known pharmacological action of the drug, known or previously reported adverse reactions to the drug or class of drugs, or judgment based on the investigator's clinical experience, the association of the event with study drug administration seems likely.

# 12.5. Assessment of Severity

The investigator will grade the severity of the AEs as mild, moderate, or severe using the following definitions:

- Mild: Symptoms causing no or minimal interference with usual social and functional activities
- Moderate: Symptoms causing greater than minimal interference with usual social and functional activities
- Severe: Symptoms causing inability to perform usual social and functional activities

# 12.6. Recording Adverse Events

All conditions present prior to the first dose of study drug should be documented as medical history. All drug-related (characterized as possibly or probably related; Section 12.4) AEs and abnormal laboratory test results reported or observed during the study must be followed to resolution (either return to baseline or within normal limits). All other AEs or non-drug-related abnormal laboratory results will be followed through the final visit (i.e., end of study or early termination). Information to be collected includes type of event, date of onset, date of resolution, investigator-specified assessment of severity and relationship to study drug, seriousness, as well as any action taken.

While an AE is ongoing, changes in the severity (e.g., worsening or improving) should be noted in the source documents but when documenting the AE, only the total duration and greatest severity should be recorded in the CRF. AEs characterized as intermittent require documentation of onset and duration.

AEs resulting from concurrent illnesses, reactions to concurrent illnesses, reactions to concurrent medications, or progression of disease states must also be reported. Pre-existing conditions (present before the start of the AE collection period) are considered concurrent medical conditions and should NOT be recorded as AEs. However, if the patient experiences a worsening or complication of such a concurrent condition, the worsening or complication (except disease progression) should be recorded as an AE. Investigators should ensure that the AE term recorded captures the change in the condition (e.g., "worsening of...").

Each AE should be recorded to represent a single diagnosis. Accompanying signs (including abnormal laboratory test values or ECG findings) or symptoms should NOT be recorded as additional AEs. If a diagnosis is unknown, sign(s) or symptom(s) should be recorded as an AE(s). Changes in laboratory test values or ECG parameters are only considered to be AEs if they are judged to be clinically significant (i.e., if some action or intervention is required or if the investigator judges the change to be beyond the range of normal physiological fluctuation). If abnormal laboratory test values or ECG findings are the result of pathology for which there is an overall diagnosis (e.g., increased creatinine levels in renal failure), only the diagnosis should be reported as an AE.

Elective procedures (surgeries or therapies) that were scheduled prior to the start of AE collection are not considered AEs. These elective procedures should not be recorded as AEs but should be documented in the patient's source documents as elective (e.g., elective periodontal

surgery). However, if a preplanned procedure is performed early (e.g., as an emergency) because of a worsening of the pre-existing condition, the worsening of the condition should be captured as an AE.

### 12.7. Reporting Serious Adverse Events

Any AE that meets the criteria of serious according to the previously described criteria must be reported within 24 hours from the time when site personnel first learn about the event. To report the SAE, fax the completed SAE form to Medpace (fax number listed below in Table 8) within 24 hours of awareness.

 Table 8:
 Serious Adverse Event Reporting Contact Information

For questions regarding SAE reporting, contact your study manager, monitor, or medical monitor:

The investigator must continue to follow the patient until the SAE has subsided or until the condition becomes chronic in nature, stabilizes (in the case of persistent impairment), or the patient dies. Within 24 hours of receipt of new information, the updated follow-up SAE form, along with any supporting documentation (e.g., patient discharge summary or autopsy reports), should be faxed to Medpace Clinical Safety (Table 8).

The Sponsor or its designee will notify regulatory agencies of any fatal or life-threatening unexpected events associated with the use of the study drug as soon as possible but no later than 7 calendar days after the initial receipt of the information. Initial notification will be followed by a written report within the timeframe established by the appropriate regulatory agency. For other SAEs that do not meet the fatal or life-threatening unexpected criteria but are reported to be associated with the use of the study drug (that is, "possible" or "probable" in causality assessment), the Sponsor or its designee will notify the appropriate regulatory agencies in writing within the timeframe established by those regulatory agencies. The Sponsor or its designee will provide copies of any reports to regulatory agencies regarding serious and unexpected SAEs to the investigators for their information and submission to their IRB/EC, as appropriate.

Principal investigators are responsible for informing their IRB/EC of any SAEs at their site, as appropriate. The DSMB will review all safety data in an unblinded manner throughout the study and make recommendations as appropriate. SAE correspondence with regulatory authorities or IRBs/ECs must be submitted to the Sponsor or its designee for recording in the study file.

# 14. STATISTICS

### 14.1. Sample Size

The sample size for Part 1 is based on a dose-escalation scheme to evaluate initial safety, PK, and PD activity of RTA 408 in this patient population. The small number of patients at each dose in Part 1 is not expected to fully characterize safety, efficacy, or PD, but rather inform the DSMB and Sponsor of the appropriate doses to select for Part 2. With 24 patients enrolled in Part 2 (8 patients per treatment cohort), this study has approximately 80% power to detect an improvement of 0.28 W/kg in the peak work of pooled RTA 408 (n=16) versus placebo (n=8) assuming a two-sided Type I error rate of 0.05, a common within-group standard deviation (SD) of 0.28 W/kg, and a drop-out rate of no more than 1 in the placebo group and no more than 2 in the pooled RTA 408 group. The analysis will use repeated measures methodology, assuming compound symmetry for the within-subject covariance structure ( $\rho$ =0.20).

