#### Statistical methods:

Sample size: The sample size for Part 1 is based on a dose-escalation scheme to evaluate initial safety and PD activity of RTA 408 in this patient population. The small number of patients at each dose in Part 1 is not expected to fully characterize safety, efficacy, or PD, but rather inform the DSMB and Sponsor of the appropriate doses to select for Part 2. With 24 patients enrolled in Part 2 (8 patients per treatment cohort), this study has approximately 80% power to detect an improvement of 0.28 W/kg in the peak work of pooled RTA 408 (n=16) versus placebo (n=8) assuming a two-sided Type I error rate of 0.05, a common within-group standard deviation (SD) of 0.28 W/kg, and a drop-out rate of no more than 1 in the placebo group and no more than 2 in the pooled RTA 408 group. The analysis will use repeated measures methodology, assuming compound symmetry for the within-subject covariance structure ( $\rho$ =0.20).

Sample size recalculation: A sample size recalculation will be performed in Part 2 after all 24 patients have been randomized to evaluate the pooled distribution of baseline peak work. If the SD for pooled, baseline peak work is greater than 0.28 W/kg or the distribution is not approximately normal, then an additional 12 patients will be enrolled in Part 2. With 36 patients enrolled in Part 2 (i.e., 12 patients per randomized treatment cohort), the 80% power is retained to detect the same difference of 0.28 W/kg if the SD is up to 0.35 W/kg, under the same assumptions of a two-sided Type I error rate of 0.05, and a drop-out rate of no more than 1 in the placebo group and no more than 2 in the pooled RTA 408 group, assuming compound symmetry for the within-subject covariance structure ( $\rho$ =0.20).

Statistical analysis: A statistical analysis plan (SAP) detailing the analyses to be performed will be developed prior to the database lock. The SAP, which will describe in detail the methods used for the primary and secondary endpoints, will serve as the final arbiter of all statistical analyses. Data will be summarized using descriptive statistics. Continuous data will be summarized with number of patients (n), mean, median, minimum, maximum, SD, coefficient of variation, and geometric mean (where applicable). Categorical data will be summarized using frequency counts and percentages.

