Primary efficacy analysis: Primary analysis of the efficacy data will be based on the modified intent-totreat population, which will include all patients enrolled in Part 2 of the study. Peak work from Part 2 for the pooled patients treated with RTA 408 (both dose levels will be compared with placebo after 12 weeks of treatment by repeated measures analysis of covariance, with treatment group, time, and the interaction between treatment and time as fixed factors and baseline peak work as a covariate. The difference between RTA 408 and placebo in change from baseline of mean peak work will be estimated along with the 95% confidence interval of the difference. The SAP will describe the strategy used to control the Type I error rate when comparing each dose of RTA 408 with placebo.

3.	TABLE OF CONTENTS AND LISTS OF TABLES A	ND FIGURES
1.	TITLE PAGE	1
2.	SYNOPSIS	5
3.	TABLE OF CONTENTS AND LISTS OF TABLES AND FIGURE	ES10
4.	LIST OF ABBREVIATIONS AND DEFINITIONS OF TERMS	16
5.	INTRODUCTION	19
5.1.	Background and Rationale for RTA 408 in Mitochondrial Myopathy	y19
6.	STUDY OBJECTIVES AND PURPOSE	
6.1.	Primary Objectives	
6.2.	Secondary Objective	
6.3.	Exploratory Objectives	
7.	INVESTIGATIONAL PLAN	
7.1.	Overall Study Design	
7.2.	Number of Patients	
7.3.	Treatment Assignment	
7.4.	Dose Selection and Escalation Scheme	25
7.4.1.	Selection of Doses	
7.4.2.	Dose-Escalation Scheme	
7.4.3.	Criteria for Determining Dose-Limiting Toxicity	
7.4.4.	Intra-patient Dose Escalation	
7.5.	Data Safety Monitoring Board	
7.6.	Criteria for Study Termination	
7.7.	Schedule of Assessments for Both Part 1 and Part 2	
8.	SELECTION AND WITHDRAWAL OF PATIENTS	
8.1.	Patient Inclusion Criteria	
8.2.	Patient Exclusion Criteria	
8.3.	Patient Rescreening	
8.4.	Patient Discontinuation and Termination	
8.4.1.	Patient Discontinuation Criteria	
8.4.2.	Patient Termination Criteria	
9.	TREATMENT OF PATIENTS	
Version 5.0	10	29 October 2015

9.1.	Description of Study Drug	34
9.2.	Prior and Concomitant Medications	34
9.2.1.	Excluded Medications	34
9.2.2.	Permitted Medications	35
9.3.	Compliance With Study Drug	35
9.4.	Randomization	36
9.5.	Blinding	36
9.5.1.	Patient Unblinding	36
9.5.2.	Unblinding for Regulatory Submission	36
9.6.	Unscheduled Visits	37
9.7.	Pregnancy	37
9.7.1.	Women of Childbearing Potential	37
9.7.2.	Methods of Birth Control	37
9.7.2.1.	Methods of Birth Control for Patients Enrolled in the United States:	37

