# 11. EFFICACY ASSESSMENTS

### **11.1. Maximal Exercise Test**

The following parameters will be collected during the maximal exercise test and analyzed from Baseline to Weeks 4 and 12: change in peak work, peak oxygen utilization, and cardiac output at selected sites.

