#### 14.1.1. Sample Size Recalculation

A sample size recalculation will be performed in Part 2 after all 24 patients have been randomized to evaluate the pooled distribution of baseline peak work. If the SD for pooled, baseline peak work is greater than 0.28 W/kg or the distribution is not approximately normal, then an additional 12 patients will be enrolled in Part 2. With 36 patients enrolled in Part 2 (i.e., 12 patients per randomized treatment cohort), the 80% power is retained to detect the same difference of 0.28 W/kg if the SD is up to 0.35 W/kg, under the same assumptions of a two-sided Type I error rate of 0.05, and a drop-out rate of no more than 1 in the placebo group and no more than 2 in the pooled RTA 408 group, assuming compound symmetry for the within-subject covariance structure ( $\rho$ =0.20).

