#### 14.3.2. Primary Efficacy Analysis

Primary analysis of the efficacy data will be based on the mITT population, which will include all patients randomized in Part 2 of the study. Peak work from Part 2 for the pooled patients treated with RTA 408 will be compared with placebo after 12 weeks of treatment by repeated measures analysis of covariance, with treatment group, time, and the interaction between treatment and time as fixed factors and baseline peak work as a covariate. The difference between RTA 408 and placebo in change from baseline of mean peak work will be estimated along with the 95% confidence interval of the difference. The SAP will describe the strategy used to control the Type I error rate when comparing each dose of RTA 408 with placebo\$

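### The 80% power claim names no time point; for the Week 12 primary comparison the protocol's own inputs give about 55% (24 patients, SD 0.28) and 57% (36 patients, SD 0.35)

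*Protocol*

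**What the plan says.** Protocol 14.1, repeated in the synopsis, states that with 24 patients in Part 2 "this study has approximately 80% power to detect an improvement of 0.28 W/kg in the peak work of pooled RTA 408" (16 patients) over placebo (8 patients). The inputs are a two-sided Type I error of 0.05, a within-group SD of 0.28 W/kg, loss of at most 2 pooled RTA 408 patients and 1 placebo patient, and a repeated measures analysis under compound symmetry with correlation 0.20.

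For the expansion to 36 patients, Protocol 14.1.1 states that "the 80% power is retained to detect the same difference of 0.28 W/kg if the SD is up to 0.35 W/kg", with the other assumptions unchanged.

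None of these places says at which visit, or over which visits, the 0.28 W/kg applies.

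Protocol 14.3.2 does give a time point for the Part 2 primary analysis: pooled RTA 408 "will be compared with placebo after 12 weeks of treatment by repeated measures analysis of covariance". The synopsis gives the same model, "with treatment group, time, and the interaction between treatment and time as fixed factors and baseline peak work as a covariate". Protocol 11.1 shows two post-baseline maximal exercise tests, with results "analyzed from Baseline to Weeks 4 and 12: change in peak work".

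**The concern.** In a model with a treatment-by-time interaction, the Week 12 treatment difference is estimated from Week 12 data. Among patients with both visits, Week 4 adds no precision to it. A low correlation between visits (0.20) helps considerably when two visits are averaged, because the average is much less variable than a single measurement. It helps hardly at all at a single visit. A power figure that relies on averaging therefore cannot be carried over to Week 12.

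The 80% figure is the stated justification for both the 24-patient size and the expansion to 36. If it does not apply to the primary comparison, a true Week 12 effect of 0.28 W/kg would be missed far more often than one time in five, and a null result in Part 2 could be over-read as evidence of no effect. As written, a reader cannot tell which comparison is powered.

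**Working it through.** **Inputs (Protocol 14.1 and 14.1.1).** Difference 0.28 W/kg; two-sided alpha 0.05; correlation ρ = 0.20.
- 24 patients: 16 − 2 = 14 vs 8 − 1 = 7, SD 0.28.
- 36 patients: 24 − 2 = 22 vs 12 − 1 = 11, SD 0.35.

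**Formula.** Noncentrality = difference / (SD × √(v × (1/n₁ + 1/n₂))). The variance factor v depends on the contrast:
- Week 12, unadjusted: v = 1
- Week 12, adjusted for baseline: v = 1 − ρ² = 0.96
- Average of Weeks 4 and 12, unadjusted: v = (1 + ρ)/2 = 0.60
- Average of Weeks 4 and 12, adjusted for baseline: v = 0.60 − ρ² = 0.56

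Power is given by noncentral t (N − 2 degrees of freedom, or N − 3 with the covariate) and by normal approximation. The adjusted factors assume that ρ = 0.20 also links baseline to the later visits.

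**Step 1: reproduce the stated 80% (two-visit average, unadjusted).**
- 24 patients: 0.28 / (0.28 × √(0.60 × (1/14 + 1/7))) = 2.789; normal power 79.6%.
- 36 patients: 0.28 / (0.35 × √(0.60 × (1/22 + 1/11))) = 2.797; normal power 79.9%.

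One contrast thus recovers both published figures, at two different sample sizes and SDs.

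**Step 2: the Week 12 comparison, adjusted for baseline.**
- 24 patients: 0.28 / (0.28 × √(0.96 × (1/14 + 1/7))) = 2.205; power 55.0% by t.
- 36 patients: 0.28 / (0.35 × √(0.96 × (1/22 + 1/11))) = 2.211; power 57% by t.

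**All variants, two-sided, with the stated dropout:**

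| Contrast | 24 patients, SD 0.28 (t / normal) | 36 patients, SD 0.35 (t / normal) |
|---|---|---|
| Week 12, unadjusted | 53.6% / 57.9% | 55.5% / 58.2% |
| Week 12, adjusted | 55.0% / 59.7% | 57% / 59.9% |
| Average, unadjusted | 75.4% / 79.6% | 77.3% / 79.9% |
| Average, adjusted | 77.9% / 82.3% | 80.0% / 82.5% |

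Two simulations of the Week 12 analysis of covariance, which include chance baseline imbalance, gave 52.8% and 53.1% (24 patients) and 55.6% and 55.8% (36 patients).

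**Step 3: can another reading rescue 80% at Week 12?**
- No dropout: at most 65.4% (16 vs 8, SD 0.28) and 63.7% (24 vs 12, SD 0.35).
- One-sided 0.05 with no dropout: at most 76.2% and 74.7%.
- SD read as the SD of change, or as a residual SD: about 54% to 56% by t.
- Unadjusted change score built from the visit SD, v = 2(1 − ρ) = 1.6: 36.8% and 38.2% by t.

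**Step 4: difference detectable with 80% power at Week 12, adjusted.**
- 24 patients: 0.376 W/kg by t, 0.356 by normal approximation.
- 36 patients, SD 0.35: 0.367 W/kg by t, 0.355 by normal approximation.

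**Step 5: sensitivity to ρ (24 patients, Week 12, adjusted, t).** 55% at 0.20, 66% at 0.5, 80% at about 0.68, 93% at 0.8. For 36 patients at SD 0.35, 80% needs ρ of about 0.66.

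**The case against.** The strongest reply is that the sponsor's arithmetic is sound: the stated inputs give 80% for the two-visit average, so what is at fault is an unnamed contrast. That stands. It does not help the plan, because 14.3.2 specifies a different contrast.

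Second, the 55% depends on ρ. The protocol gives 0.20 for the repeated measures and does not say that it also links baseline to Week 12. If the true correlation is near 0.7, the study is adequately powered. This also stands as a caveat, but 0.20 is the protocol's own value, no document reports an observed one, and power with no credit for baseline adjustment is still 54%.

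Third, the 57% for 36 patients applies at the SD ceiling of 0.35. Expansion can also be triggered by a non-normal distribution with a smaller SD. At 22 vs 11 and SD 0.28, Week 12 adjusted power is 76% by t, so expansion does help in that case.

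Fourth, the supplied SAP covers Part 1 only. Its section 2 places the Part 2 analyses in a separate document, and Protocol 14.3 makes the SAP the final arbiter. Protocol 14.3.2 also refers loosely to change in mean peak work, which could be read as an average. But the sentence before it fixes the comparison at 12 weeks, and the power claim itself sits in the protocol. SAP section 2 also describes Part 2 as using one dose, whereas the protocol pools two. Those passages need to be reconciled, and a one-dose design would need its own calculation.

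Finally, this is a Phase 2 study and the remedy is disclosure. That bears on how serious the point is, but a gap of about 25 percentage points goes beyond what the word approximately can cover.

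**Conclusion.** The concern holds and should be corrected. At the protocol's own assumptions, power for the Week 12 primary comparison is about 55% with 24 patients at SD 0.28 W/kg, and about 57% with 36 patients at SD 0.35 W/kg. Reasonable two-sided methods give 53% to 60% and 56% to 60%. A true Week 12 effect of 0.28 W/kg would be missed about 45% of the time with 24 patients, rather than 20%. The detectable difference of about 0.38 W/kg is roughly a third larger than stated (0.376 / 0.28 = 1.34).

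The conclusion rests on ρ = 0.20, on the stated dropout, and on reading 14.3.2 as a Week 12 contrast. With no dropout at all, the two-sided shortfall remains. That the 80% came from averaging Weeks 4 and 12 is inferred from the match in both scenarios; the protocol does not say so.

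**What to change.** In Protocol 14.1, 14.1.1 and the synopsis:
- Name the contrast to which the power refers.
- For the baseline-adjusted Week 12 comparison at ρ = 0.20, state power of about 55% and a detectable difference of about 0.38 W/kg (24 patients, SD 0.28), and about 57% and 0.37 W/kg (36 patients, SD 0.35). The 76% case (36 patients, SD 0.28) is a useful addition.
- State that ρ is taken to apply between baseline and Week 12, and show power over a range of ρ, using the Part 1 estimate if available.
- If 80% is meant for the average of Weeks 4 and 12, say so and attach it to that contrast only.

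The cost is wording in three places and a less favourable figure at ρ = 0.20; the restatement needs no added patients. If the sponsor instead wants 80% at Week 12 with ρ = 0.20, it would need about 36 evaluable patients (24 vs 12) at SD 0.28, or about 57 (38 vs 19) at SD 0.35, before any allowance for dropout.
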